**CONFIDENTIAL**

215301 (EARLY-CLINRES-017)

CCI

CCI

No dropout is assumed for the post-dose 1 evaluation.

## **6. SUPPORTING DOCUMENTATION**

### **6.1. Appendix 1 Study Population Analyses**

#### **6.1.1. Participant Disposition**

The number of participants who are enrolled, vaccinated and in each study group will be tabulated.

In addition, the number of participants in each analysis set will be described, e.g., including the number of participants excluded from the PPS and the number who withdraw and reason for dropout.

### **6.1.2. Demographic and Baseline Characteristics**

N, mean, SD, median, minimum and maximum of age (in years) at first vaccination, height (cm), weight (kg), and body mass index (BMI) (kg/m^2) will be computed by group. Participants composition by country, center, sex, race, ethnicity category will be summarized overall and by study group. This analysis will be based on the ES and the PPS.

### **6.1.3. Participant exposure**

The number and percentage of participants who received each study intervention will be tabulated by group and by dose for the ES.

### **6.1.4. Concomitant Medications**

Medications will be coded using the GSKDRUG dictionaries.

The number and percentage of participants using concomitant medication (any medication and any antipyretic) during the 14-day and the 31-day follow-up period after each dose and overall will be tabulated with exact 95% CI.

## **6.2. Appendix 2 Electronic Clinical Outcome Assessment (eCOA) Compliance**

### **6.2.1. eDiary data**

- In this study, solicited events are collected via electronic diary (eDiary).
- When the participant fills in the eDiary, on each day he/she has to fill in all the solicited symptoms in order to be able to submit the daily eDiary entry, during the 14-day follow-up period after each dose.
- Along with the presence of solicited events, participants are required to report symptom intensity. For erythema and swelling, the maximum diameter has to be reported. For temperature, participant has the option of providing the value of temperature in degrees or report it as « Unable to measure ». In both cases, the reporting of temperature will be considered as completed.
- In case of missed entries by the participant, the investigator should contact the participant and report missing data into eCRF. In case of erroneous participant entries, these are corrected via Data Correction Form (DCF) in the e-Diary platform. There was no time constraint for missing data entry or correction foreseen at study start and there is no available information of actual date and time of missing/corrected data collection by the investigator in the database.

- The completion level is defined:
  - Based on eDiary data filled in by the participant (including possible corrections via DCF).
  - Based on data including also information entered by the investigator via missed solicited events page in eCRF.
- For the completion level **within 14-day follow-up period after each dose**:
  - For daily **completion level** calculation:
    - Denominator will be the total number of **eDiaries expected** to be completed by all dosed participants for the given observation day.
    - Numerator will be the number of **eDiaries effectively completed** by the dosed participants for the given observation day.
  - **Overall completion** level for the 14-day follow-up period after each dose:
    - Denominator\* will be the total number of eDiaries expected to be completed by dosed participants for the entire 14-day follow-up period after each dose.
    - Numerator will be the number of eDiaries effectively completed by dosed participants during the entire 14-day follow-up period after each dose.

\*For the denominator, if the monitoring is performed with data up to 22 May 2024 for example, a participant who received Dose 1 on 20 May is expected to have an eDiary completed for Day 1 and Day 2, but not yet for Day 3 up to Day 14.

- For solicited events **ongoing after the 14-day follow-up period after each dose**, eDiary will continue to be filled for each individual ongoing symptom for each participant. As soon as the intensity of an ongoing symptom is reported as 'None', the symptom is considered as ended.
  - Completion level calculation beyond the solicited follow-up period (15-31 days post each dose):
    - Denominator will be the total number of expected **eDiaries** (i.e., the total number of individual eDiaries for all ongoing symptoms for all participants for symptoms reported on the previous day, Day 14 or beyond).
    - Numerator will be the total number of **eDiaries** that have been completed.

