**Table 1      Study interventions**

	Study intervention 1	Study intervention 2	Study intervention 3	Study intervention 4	Study intervention 5
Study intervention name:	Engerix-B	HBsAg/AS03A	Fendrix	HBsAg/AS37B*	HBsAg/AS37A**
Group label	HBs-Alum	HBs-AS03	HBs-AS04	HBs-AS37_50	HBs-AS37_100

\*AS37B refers to aluminum hydroxide + 50 µg CCI [REDACTED]

\*\*AS37A refers to aluminum hydroxide + 100 µg CCI [REDACTED]

- Variable / endpoint:
  - Occurrence of events reported within protocol-defined safety follow-up period.
  - Absolute values post-Dose 1 and 2 and changes from baseline in hematology and biochemistry parameters
- Summary measure:
  - Percentage of participants reporting events within protocol-defined safety follow-up period.
    - For solicited events, the participants not completing the diary are not considered in the denominator (see [Section 6.3.2](#) for details).
    - For unsolicited events, participants not reporting events are considered to be participants without event (see [Section 6.3.2](#) for details).
  - Summary statistics of absolute values post-Dose 1 and 2 and changes from baseline in hematology and biochemistry parameters as well as percentage of participants with abnormal laboratory parameter values, based on the Food and Drug Administration (FDA) grading as presented in Table 22 of the study protocol.

[figure not shown]

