### 4.2. Primary Endpoints Analyses

#### 4.2.1. Analysis of safety planned in the protocol

The primary endpoints will be based on the reactogenicity and safety objectives and will be performed on the ES. Below the follow-up period for solicited AEs is intended for Dose 1 and Dose 2 only and not Dose 3.

- The percentage of participants reporting at least one solicited adverse event (AE), at least one solicited administration site AE, and at least one solicited systemic AE during the 14-day follow-up period (i.e., the day of vaccination and 13 subsequent days) will be tabulated for each group after each dose and overall. For solicited AEs, percentages will be computed based on the total number of solicited symptoms screens completed.
- The number and percentage of participants reporting each individual solicited AE during the 14-day follow up period post-vaccination (i.e., the day of vaccination and 13 subsequent days) will be tabulated with exact 95% CI and descriptive statistics for each group, after each dose and overall.
- The number and percentage of participants reporting each individual solicited administration site AE (any grade, Grade 3 and resulting in medically attended visit) and solicited systemic AE (any grade, Grade 3 and resulting in medically attended visit) during the 14-day follow-up period (i.e. the day of vaccination and 13 subsequent days) will be tabulated for each group, after each dose and overall.

- The number and percentage of participants with each solicited administration site event and separately, solicited systemic event (any grade and grade 3) within the 14-day follow up period will be represented graphically with a bar plot for each group and after each dose.
- The duration of each individual solicited AE during the 14-day follow-up period will be tabulated using descriptive statistics (mean, minimum, Q1, median, Q3, maximum). The same computations will be done for Grade 3 solicited events. This analysis will be done for each group after each dose.

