### **6.2.2. Endpoint Level Completion analysis**

The completion level will be measured, daily and overall:

- Within 14-day follow-up period after each dose after each dose.
- Beyond the solicited follow-up period (i.e., 15-31 days post each dose)

and based on

- eDiary data filled in by the participant (including possible corrections via DCF).
- Data including also information entered by investigator via missed solicited events page in eCRF.

Because on each day participants have to fill in all the solicited symptoms in order to be able to submit the daily eDiary entry, completion level will be identical for all symptoms. The completion level will therefore be summarized once for symptoms, by study group and dose, as well as overall (across the 2 doses), using frequency tables.

The number of participants who have 0 to <50% overall completion level, 50 to <80% overall completion level, and  $\geq 80\%$  overall completion level of eDiary assessments will be summarized too, by study group and dose, as well as overall.

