#### **6.3.2.5. Daily recording of solicited events**

##### **6.3.2.5.1. Studies with electronic diaries**

As this study uses electronic diaries for the collection of solicited AEs, a solicited AE will be considered present only when a daily recording of grade 1 or more is present. Missing or non-evaluable measurements will not be replaced.

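### Followed as written, the SAP keeps a participant with no measured temperature in the fever denominator as a non-event, and its completion summary cannot show how often this happens

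*SAP*

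**What the plan says.** SAP 6.2.1 (eCOA compliance appendix) describes the temperature item: the "participant has the option of providing the value of temperature in degrees or report it as" 'Unable to measure'. It then states the status of the two kinds of entry: "In both cases, the reporting of temperature will be considered as completed".

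Three rules elsewhere in the SAP determine the fever percentage:

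- **Numerator**, SAP 6.3.2.5.1: "a solicited AE will be considered present only when a daily recording of grade 1 or more is present". The next sentence adds: "Missing or non-evaluable measurements will not be replaced".
- **Denominator**, SAP 4.2.1: "For solicited AEs, percentages will be computed based on the total number of solicited symptoms screens completed".
- **Denominator in the primary estimand**, SAP 1.1: "For solicited events, the participants not completing the diary are not considered in the denominator".

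SAP 6.2.2 reasons that every symptom must be filled in before a day can be submitted, so "completion level will be identical for all symptoms", and completion is therefore summarised once for all symptoms.

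**The concern.** Temperature is the one solicited item for which the SAP describes a non-answer that still counts as complete. The SAP has no sentence on how such an entry enters the fever analysis, so the general rules apply. Those rules bar the day from the numerator but give no ground for removing the participant from the denominator.

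Fever is a solicited systemic event (Protocol 10.3.3) and so belongs to the primary reactogenicity endpoint. It was also among the severe systemic events reported with the 100 µg formulation in the earlier study (Protocol 2.3.1), and the possible higher reactogenicity of that formulation is the stated reason for staggered dosing. If unmeasured temperatures were more common in one group, the comparison of fever between groups could be affected, and the planned completion tables would still show full completion in every group.

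**Working it through.** The documents give no fever rate and no frequency of 'Unable to measure', so there is no planned figure to reproduce. The check traces the rules and then shows the size under assumed counts.

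**1. Inputs from the documents.** Follow-up is 14 days after each of Dose 1 and Dose 2 (SAP 4.2.1). An event counts once per participant per period, however many days it occurs (SAP 6.3.3.7). Groups have 23 to 30 participants (SAP 5). Individual solicited events are reported with exact 95% CIs (SAP 4.2.1). I read the denominator in SAP 4.2.1 at participant level, as SAP 1.1 does.

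**2. What the rules give for a participant who submits all 14 diary days.**

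| Temperature record | In numerator | In denominator | Completion |
|---|---|---|---|
| Fever, at least one febrile day measured | Yes | Yes | 14/14 |
| Fever, every febrile day unmeasured, other days measured | No | Yes | 14/14 |
| No temperature measured on any day | No | Yes | 14/14 |
| All days measured, no fever | No | Yes | 14/14 |

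The last three rows cannot be told apart in the planned fever and completion outputs. In the first row, fever is counted, but if the peak day was unmeasured the maximum grade may be too low.

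**3. What the completion figure hides.** With k unmeasured days among 14 submitted, completion stays 14/14 = 100%, while the share of days with a measured temperature is (14 − k)/14:

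- k = 1: 92.9%
- k = 4: 71.4%
- k = 7: 50.0%
- k = 14: 0%

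All four participants fall in the top completion band of SAP 6.2.2 (80% or more).

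**4. A fever missed because every febrile day is unmeasured.** Assume a fever lasts d days and each day is unmeasured with probability q, independently. Then P(missed) = q^d, and a true rate of 20% (assumed) shows as 20% × (1 − q^d):

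| q (assumed) | d = 1 | d = 2 |
|---|---|---|
| 2% | 19.6% | 19.99% |
| 5% | 19.0% | 19.95% |
| 10% | 18.0% | 19.8% |
| 20% | 16.0% | 19.2% |

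The loss is nearly confined to one-day fevers. Independence is a simplification. If participants skip measurement because they feel ill, unmeasured days cluster on febrile days and the loss is larger.

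**5. Participants with no measured temperature at all.** Assume 5 recorded fevers and u never-measured participants. The planned rate is 5/n, the rate among those measured is 5/(n − u), and the upper bound if all u had fever is (5 + u)/n. Clopper-Pearson 95% CIs are in brackets.

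| n | u | Planned | Among measured | Upper bound |
|---|---|---|---|---|
| 23 | 1 | 21.7% (7.5 to 43.7) | 22.7% (7.8 to 45.4) | 26.1% (10.2 to 48.4) |
| 23 | 2 | 21.7% (7.5 to 43.7) | 23.8% (8.2 to 47.2) | 30.4% (13.2 to 52.9) |
| 23 | 3 | 21.7% (7.5 to 43.7) | 25.0% (8.7 to 49.1) | 34.8% (16.4 to 57.3) |
| 30 | 1 | 16.7% (5.6 to 34.7) | 17.2% (5.8 to 35.8) | 20.0% (7.7 to 38.6) |
| 30 | 2 | 16.7% (5.6 to 34.7) | 17.9% (6.1 to 36.9) | 23.3% (9.9 to 42.3) |
| 30 | 3 | 16.7% (5.6 to 34.7) | 18.5% (6.3 to 38.1) | 26.7% (12.3 to 45.9) |

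For n = 23 and u = 2, the choice of denominator moves the estimate by 23.8 − 21.7 = 2.1 percentage points, well inside either interval.

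**The case against.** The sentence in SAP 6.2.1 belongs to a compliance appendix. It defines diary completion and assigns no grade. A reader might infer that the SAP recodes an 'Unable to measure' day to grade 0, in other words to no fever. The documents do not support that: SAP 6.3.2.5.1 leaves non-evaluable measurements unreplaced, and no sentence addresses a participant whose entries are all of this kind. This objection stands. The non-event status is the combined effect of four rules and is nowhere stated as a rule.

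A reader might also infer that fever will be understated in this trial. That is not shown either. Fever is counted per participant, so one unmeasured day changes nothing if another febrile day was measured or if there was no fever. If the never-measured participants were afebrile, the planned percentage is right and excluding them overstates fever.

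Diary data are reviewed at repeated visits and calls (Protocol 1.3 and 10.3.8), so a wholly unmeasured window might be noticed. That makes the extreme case less likely. However, the follow-up route in SAP 6.2.1 covers missed and erroneous entries, and nothing says that an 'Unable to measure' entry triggers it.

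The completion statement in SAP 6.2.2 is true of screen submission, so deleting it would be wrong. A denominator of participants with at least one measured temperature also does nothing for someone whose only unmeasured days were the febrile ones; a count of those days is needed too.

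Finally, the rationale for Protocol Amendment 4 refers to results already obtained in the main analysis, and that analysis covers reactogenicity data to Day 61 (Protocol 9.4.1.1). Replacing the fever denominator now would be a post hoc change to a primary endpoint in an open-label study. This stands, and it is why the alternative percentage belongs beside the planned one.

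**Conclusion.** The concern holds in a limited form. A participant with no measured temperature in the window stays in the fever denominator as a non-event, fever on unmeasured days cannot be counted, and no completion output shows how often either occurs. The gap in completion reporting follows directly from the text. The denominator effect rests on reading SAP 1.1, 4.2.1, 6.2.1 and 6.3.2.5.1 together.

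The size cannot be derived from the documents and is probably small. At two never-measured participants among 23 with five recorded fevers, all assumed, the shift is 2.1 percentage points, or at most 30.4 − 21.7 = 8.7 points if both had fever. All analyses are descriptive, so no test result is at stake. This is a minor point of clarity and transparency in a primary safety endpoint.

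**What to change.** 1. In SAP 6.3.2.5.1, state that 'Unable to measure' is a missing temperature for the fever analysis.
2. Report the fever percentage among participants with at least one measured temperature in the 14-day window after the dose, alongside the planned percentage and labelled as an addition made after the main analysis.
3. Tabulate 'Unable to measure' days by group, dose and day. This shows whether they cluster on the days when fever is expected, which a change of denominator cannot show.
4. Qualify SAP 6.2.2: completion is identical across symptoms for screen submission, but not for measured temperature.

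The response option already exists in the eDiary, so no new data collection is needed. The cost is a few SAP sentences and one extra table column. The added percentage has a slightly smaller denominator and would slightly overstate fever if the unmeasured participants were afebrile, so the two percentages should be read together.

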### **6.2.3. Study level compliance**

No study level eCOA compliance will be calculated because the only eCOA foreseen to be followed up in the statistical outputs is the eDiary.

Quality Tolerance Limit on eDiary completion are defined separately from this SAP and are not in scope of this evaluation.

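### As written, SAP 6.2.1 drops the day after a missed entry from the Day 15-31 eDiary denominator, so an episode closed by 'None' scores 100% however many days were missed

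*SAP*

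**What the plan says.** SAP 6.2.1 sets out what happens when a solicited symptom is still present at the end of the 14-day period: "eDiary will continue to be filled for each individual ongoing symptom for each participant". It gives one way for the symptom to end: "As soon as the intensity of an ongoing symptom is reported as 'None', the symptom is considered as ended". Taken together, these make a diary due on each day until 'None' is entered, within the Day 15-31 window used in SAP 6.2.1 and 6.2.2.

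The completion formula that follows uses a different idea of what is due. Its denominator is "the total number of individual eDiaries for all ongoing symptoms for all participants for symptoms reported on the previous day, Day 14 or beyond". Its numerator is introduced by "Numerator will be the total number of" and refers to completed eDiaries, with no restriction to those counted as expected.

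For Days 1-14 there is no previous-day condition. The overall denominator there is "the total number of eDiaries expected to be completed by dosed participants for the entire 14-day follow-up period after each dose".

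SAP 6.2.2 asks for completion daily and overall, in two versions. One uses participant entries (with corrections); the other is described as "Data including also information entered by investigator via missed solicited events page in eCRF". It also bands participants by overall completion: below 50%, 50% to below 80%, and 80% or more. No section says how the day after a missed day is to be counted.

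**The concern.** A missed day carries no report. Under the denominator rule the next day is then not expected, although under the SAP's own end rule the symptom is still running. In a run of missed days only the first is charged. When entries resume, the first one enters the numerator without a matching day in the denominator.

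At stake is whether the Day 15-31 completion table, given by group and dose, means what its label says. Gaps are what such a table should reveal, and this rule hides most of them. Groups with more prolonged symptoms and longer gaps would be distorted most. The two definitions in 6.2.1 also leave room for two programmers to produce different tables from the same data.

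**Working it through.** The SAP gives no completion figure, so there is nothing to reproduce. The check applies the rule directly.

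**Notation.** Take a symptom reported on Day 14. C_d = 1 if the diary for day d is completed and 0 if not, so C_14 = 1. E is the day 'None' is reported, or Day 31 if it never is. Sums run over d = 15 to E.

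- Completed diaries: N = ΣC_d.
- SAP denominator (previous day reported): D = ΣC_(d-1) = C_14 + N - C_E = N + 1 - C_E.
- Comparison denominator under the SAP's own end rule: F = E - 14, at most 31 - 14 = 17.

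**What follows.** If the episode closes with a reported 'None', C_E = 1, so D = N and the score is 100%. If Day 31 is reached without an entry that day, the score is N/(N + 1). D counts a subset of the F days, so N/D is never below N/F. This identity uses no assumed missed-day rate.

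**Single episodes**

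| Entries after Day 14 | SAP as written | Numerator confined to counted days | Every day to 'None' or Day 31 |
|---|---|---|---|
| Days 16-20 missed, 'None' on Day 24 | 5/5 = 100% | 4/5 = 80% | 5/10 = 50% |
| Day 15 missed, 'None' on Day 17 | 2/2 = 100% | 1/2 = 50% | 2/3 = 67% |
| Day 15 only, then nothing | 1/2 = 50% | 1/2 = 50% | 1/17 = 6% |
| Days 16, 18, ... 30 only | 8/9 = 89% | 0/9 = 0% | 8/17 = 47% |
| Nothing | 0/1 = 0% | 0/1 = 0% | 0/17 = 0% |

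In the first row the completed days are 15, 21, 22, 23 and 24. The days counted as expected are 15, 16, 22, 23 and 24. Day 21 is in the numerator only, and Days 17-20 appear nowhere.

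**Daily figure.** Suppose three participants have the symptom on Day 14. Two enter Days 15 and 16; the third misses Day 15 and enters Day 16. For Day 16 the numerator is 3 and the denominator 2, giving 150%.

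**Pooled figure (assumed example).** Eight episodes are complete and closed on Day 18 (4 diaries each, 32 in all), and two have no entry after Day 14. The SAP rule gives 32/(32 + 2) = 94%, whether or not the numerator is confined. Charging the two to Day 31 gives 32/(32 + 2×17) = 32/66 = 48%. Charging them to Day 18 gives 32/(32 + 2×4) = 32/40 = 80%.

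**Simulation (assumed missed-day patterns, not in the documents).** There were 100,000 episodes per row. 'None' was due on Day 20 and reported at the first completed day from then on. In the rows with runs, a missed day was followed by another with probability 75%.

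| Missed days | SAP as written | Numerator confined | Every day |
|---|---|---|---|
| 20%, independent | 100% | 80% | 80% |
| 40%, independent | 100% | 60% | 60% |
| About 20%, in runs | 99.9% | 94% | 80% |
| About 40%, in runs | 99.6% | 83% | 60% |

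**The case against.** The strongest reply is that a completion level normally means completed among expected. On that reading, independent misses cause no average bias, isolated misses are understated, and the alternate-day example falls to 0/9 instead of rising to 8/9. This stands as a limit: overstatement is not universal under every reading. But the SAP does not state that restriction, and with it runs of missed days are still overstated.

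Second, once entries stop, nobody knows whether the symptom persisted. Counting to Day 31 is a convention, and the 48% and 80% in the pooled example show how much it matters. This also stands. Seventeen days is a ceiling, too. With Dose 2 on Day 31, Days 15-30 leave 16. With Dose 2 at the earliest allowed interval of 21 days (Day 22), Days 15-21 leave 7.

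Third, other outputs help. The version with investigator entries restores previous-day reports where gaps are filled. Someone who stops right after Day 14 scores 0% under either rule, and the Day 15 daily figure shows that loss. These outputs reduce the problem but do not correct the pooled participant-only figure.

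Fourth, the wording about all ongoing symptoms might be read as keeping a symptom in the denominator until 'None', and how the eDiary prompts is left to the Study Procedures Manual (Protocol 10.3.8). But the text in parentheses limits the count to the previous day's reports, so the sentences still need reconciling.

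A reader might go further and infer that the primary duration endpoint is compromised. The documents do not support that. SAP 4.2.1 tabulates duration within the 14-day period. The added first-to-last-day measure in SAP 6.3.3.6 might reach past Day 14, but it does not use the completion level. Nor are these diaries the only record: investigators enter missed data (SAP 6.2.1), continuing solicited events are stored in the adverse events domain (SAP 6.3.3.8), and unresolved events are reviewed at later contacts (Protocol 10.3.8.2.1).

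**Conclusion.** The Day 15-31 completion rule is wrong as written: it contradicts the end rule in the same section and returns 100% for any episode reported on Day 14 and closed by 'None'. That result rests on the literal text alone. The size of the distortion in practice depends on the missed-day pattern, which the documents do not give. Under the assumed patterns the literal rule shows about 100% where 60% to 80% of days were completed.

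The consequence is small. The table is descriptive, and SAP 6.2.3 adds that "Quality Tolerance Limit on eDiary completion are defined separately from this SAP and are not in scope of this evaluation", so no effect on tolerance limits can be inferred from the SAP. If the completion bands apply to this period, which SAP 6.2.2 does not say outright, a participant with the first pattern in the table moves from the middle band to the top one, and a participant with the third moves from the lowest to the middle.

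**What to change.** Replace the denominator sentence in SAP 6.2.1 with a rule along these lines. For each symptom ongoing at Day 14, one diary is expected per day from Day 15 until the first day on which 'None' is reported, or until Day 31, withdrawal or the day before the next dose, whichever comes first. The numerator counts completed diaries among those days only. Where entries stop without 'None', use the investigator-recorded end date if there is one. Otherwise count to the end of the window and label the result a conservative lower bound. The rule should also say when a symptom counts as ongoing if the Day 14 entry itself is missing, because at present such a symptom does not enter until it is reported again.

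The cost is one short SAP change and a small programming change, with no new data. The reported level becomes less favourable, and it may understate completion for symptoms that resolved without a report.
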